Modulation of Pain in Fibromyalgia with rTMS at dACC and DLPFC: Several groups have investigated the analgesic effect rTMS in FMS related pain (11). In a recent study, sixteen FMS patients received 20 rTMS sessions over a 4-week period. The primary outcome measure was the Brief Pain Inventory (BPI) item 5 rating ("average pain rating in the last 24 hours" expressed on a 11-point numeric rating scale with "0" being "no pain" and "10" being "worst pain imaginable") measured 4 weeks after the last modulation session. It was demonstrated that there was up to an 84% decrease in pain ratings (average decrease 31%) after active TMS when stimulating at 10 Hz compared to a control group which was stimulated with 1 Hz. L-DLPFC rTMS can be utilized in the modulation of fibromyalgia(78) with improvements in measures of pain (66). In these studies, the stimulation parameters were 10 Hz with a pulse train duration (on time) 5 seconds, power (intensity) level 120% of resting motor threshold, and an inter-train interval (off time) 10 seconds (15 second cycle time). The primary outcome measure for this study was also the Brief Pain Inventory (BPI) item 5 rating. Excitatory L-DLPFC rTMS was shown to demonstrate a mean 29% (statistically significant) reduction in pain symptoms in comparison to the FMS patient's baseline pain. Sham rTMS participants had a 4% non-significant change in daily pain from their baseline pain(66). Inhibitory rTMS over the dACC was demonstrated to not exert a clinically meaningful effect on pain, suggesting that outside of hypnosis, inhibitory rTMS alone should not exert an independent effect on pain(11).

Intervention Regimen: We will employ a spaced continuous theta-burst technique that is capable of providing a change in neural activity, which will last for the entirety of each of the participant's

post-rTMS scanner sessions(27-30, 79).

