This aim explores if active rTMS + HA will have produce greater anti-nociceptive effects on pain thresholds than sham rTMS. Inhibitory rTMS (cTBS) will be applied to L-DLPFC and it is expected that the stimulation-induced augmentation of hypnotic analgesia will be greater in the active rTMS condition over the sham rTMS condition. It is expected that the strength of this correlation will be greater than in the active rTMS + HA condition versus sham rTMS + HA given that the hypothesis is that the rTMS will increase fc between L-DLPFC and dACC which is believed to transiently modulate these participants to have similar response to hypnotic analgesia as do high hypnotizables(31) given the 0.6 correlation between measured hypnotizability and the ability to achieve hypnotic analgesia. HA network activation/connectivity to painful thermal stimulation will be assessed at baseline, during pre-rTMS hypnotic analgesia, after rTMS, and during post-rTMS HA. Changes in mean pain ratings between baseline pain and active rTMS + HA (TBS) and sham rTMS + HA conditions will be compared using ANOVA. It is expected that there will be a significantly greater mean decrease in pain ratings with the active rTMS + HA than the sham rTMS + HA condition at the $p < 0.05$, level.

Relevant Clinical Hypothesis: *Active, inhibitory rTMS over DLPFC will enhance hypnotic analgesia as compared to sham rTMS.*

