This aim explores if L-DLPFC rTMS modulated increase in hypnotizability will have downstream effects on the hypnotic analgesia modulation of the rest of the hypnotic analgesia network (ACC, insula and/or the somatosensory cortex) by strengthening the activations/deactivations induced by HA as well as strengthening the functional connectivity induced by HA.

Hypnosis Scans for Secondary Outcome Measure D: The participants will have a baseline scan with baseline pain induction in the scanner. For this scanning session, task fMRI data will be collected while participants are randomized to receive and rate painful thermal stimulations after either active rTMS (cTBS) + hypnotic analgesia (HA) or sham rTMS + hypnotic analgesia. The differences in pain ratings and regional brain activity of the networks related to hypnotic analgesia (restricted to masks of the insula, somatosensory, L-DLPFC, and anterior cingulate cortices) as well as analyzing the functional connectivity changes between dACC and the L-DLPFC, insula, somatosensory cortices as well as between L-DLPFC and the dACC, insula, and somatosensory cortices will be analyzed. Given the relative mechanistic independence of these two putative interventions (rTMS and HA)(37, 68), it is possible that active rTMS would also directly affect analgesia, although unlikely given stimulation frequency. Certainly the downstream neural network effects of both interventions have overlapping and non-overlapping brain regions that are specific to the intervention(37, 68). rTMS, however, has been demonstrated to reach what were previously thought to be non-connected regions of a given neural network in a given condition or state(46). It is possible that rTMS alone may activate certain network nodes in one state, but in a different mental state activate other network nodes(125). This study strives to determine if rTMS modulation of hypnotizability can produce the downstream effect of increasing functional connectivity and decreasing activation of anterior cingulate, insular, and somatosensory cortices, which are areas involved in the HA network(37).

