fMRI Preprocessing and Analysis: All fMRI data will be preprocessed and analyzed using FSL (FMRIB Software Library, version 5.0) and in the manner described in the analysis description for the Primary Outcome Measure. For group analysis, FMRIB's local analysis of mixed effects will be used within a mask of our a priori ROIs (L-DLPFC, dACC, insula, and somatosensory cortices), thresholded using family-wise error (FWE) corrected $Z > 2.3$; cluster $p < 0.05$. Average contrast of parameter estimate values will be extracted from our ROIs and Spearman's correlations will be calculated between these values and differences in active versus sham rTMS.

Secondary Hypothesis E: *Active, inhibitory rTMS over DLPFC will modulate the neural network that underlies hypnotic analgesia by producing a decrease in activity and an increase functional connectivity among the anterior cingulate, dorsolateral, insular, and somatosensory cortices (hypnotic analgesia network) as compared to sham rTMS.*

The neural network involved with HA (anterior cingulate, dorsolateral prefrontal, insular, and somatosensory cortices) will be assessed at baseline (after pre-TMS hypnotic analgesia instruction) hypnosis and after rTMS (again after hypnotic analgesia instruction). Activation/deactivation as well as connectivity between baseline and post-TMS will be contrasted to determine if only the active rTMS condition results in greater reductions of activity within the network involved in hypnotic analgesia(6, 37) in comparison to sham rTMS. Changes in activity and connectivity between baseline scan and HA + active DLPFC rTMS and HA + sham rTMS conditions will be compared using ANOVA. We expect a significantly greater mean decrease in

activity and increase in connectivity with the HA + active rTMS conditions than the HA + sham rTMS condition at the $p < 0.05$, level.

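### The planned comparison of pain ratings estimates the effect of rTMS on pain under hypnosis; it equals enhanced hypnotic analgesia only if rTMS alone leaves pain unchanged, and no planned pain contrast examines that

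*Combined protocol and SAP*

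**What the plan says.** The Relevant Clinical Hypothesis in section 9.6.1 of the combined protocol is that active rTMS enhances hypnotic analgesia (HA), by raising hypnotizability. The section opens with thresholds: "This aim explores if active rTMS + HA will have produce greater anti-nociceptive effects on pain thresholds than sham rTMS". For ratings it then states: "Changes in mean pain ratings between baseline pain and active rTMS + HA (TBS) and sham rTMS + HA conditions will be compared" by ANOVA at the 0.05 level. A later paragraph proposes linear mixed models for temperature outcomes. It includes two statements about response after active versus sham rTMS that do not mention hypnosis, but it writes out no model terms and no hypnotic versus non-hypnotic contrast.

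On a direct effect of rTMS on pain, section 2.2 says: "Inhibitory rTMS over the dACC was demonstrated to not exert a clinically meaningful effect on pain", and continues: "suggesting that outside of hypnosis, inhibitory rTMS alone should not exert an independent effect on pain". Section 9.6.2, under Secondary Outcome E, is less firm: "it is possible that active rTMS would also directly affect analgesia, although unlikely given stimulation frequency". It adds: "It is possible that rTMS alone may activate certain network nodes in one state, but in a different mental state activate other network nodes".

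Sections 6.2.2 and 6.2.5 plan thermal pain runs with hypnotic and with non-hypnotic audio, before and after rTMS, at the same temperature. Run order is randomised and kept the same pre and post. Both sections describe brain responses in these runs and do not mention ratings. Secondary Outcome E mentions rating only after rTMS plus HA.

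Sections 1.1 and 9.7 name change in pain threshold as the clinical outcome. The stand-alone SAP covers only the HIP scores and the test of the blind.

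**The concern.** The hypothesis is about a difference in what hypnosis achieves. The rating test measures a difference in pain while hypnosis is present in both arms. If rTMS changes thermal pain by itself, that effect enters the result in full and would be reported as enhanced hypnotic analgesia. A direct effect in the opposite direction would hide a true enhancement. The assumption that rules this out is inferred from dACC stimulation, whereas this trial stimulates L-DLPFC. The design includes runs that bear on the question, but neither document plans a pain analysis that uses them in this way.

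**Working it through.** **Plan's own figure.** Section 9.2 gives no power for the clinical hypothesis. Its one power figure (0.8, for d = 0.8 with 40 per arm, two-sided 0.05) is for connectivity. On those inputs a noncentral t gives 0.94. That is a separate matter and is not used below, except that 40 usable per arm and two-sided 0.05 are taken from there.

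**What each comparison estimates.** Let D be the reduction in pain rating caused by active versus sham rTMS without hypnosis, and I the extra reduction under hypnosis. Both are in SDs of the pre-to-post change.

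- Planned rating test (hypnotic runs): D + I.
- Between-arm change in non-hypnotic runs: D.
- Difference of the two: (D + I) − D = I, the enhancement.

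The planned test equals I only when D = 0.

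**The choice of baseline does not remove D.** Section 9.6.1 lists baseline apart from the pre-rTMS hypnotic run (network measures "will be assessed at baseline, during pre-rTMS hypnotic analgesia, after rTMS, and during post-rTMS HA"). Section 9.6.2 uses the word for the run after hypnotic instruction ("will be assessed at baseline (after pre-TMS hypnotic analgesia instruction) hypnosis and after rTMS (again after hypnotic analgesia instruction"). Either way the baseline precedes stimulation, so randomisation gives the arms the same expected value and the expected between-arm difference stays D + I. Only the within-arm change and the precision differ.

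**Size if D is not zero (D and I assumed; the documents give none).** Power is from the noncentral t with df = 2n − 2 and noncentrality d√(n/2).

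- I = 0, n = 40, D = 0.2, 0.3 or 0.5: noncentrality 0.89, 1.34 or 2.24; rejection 0.143, 0.263 or 0.598. Over 40 to 50 per arm: 14–17%, 26–32%, 60–70%.
- I = 0.5 with an opposite D of 0.2 or 0.3: net effect 0.3 or 0.2, so power falls from 0.60 to 0.26 or 0.14.
- D = 0: the planned test is unaffected.

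**Precision of the contrast for I.** Let ρ be the between-person correlation of the changes in the two run types, with equal SDs assumed. The contrast variance is 2(1 − ρ) times that of the planned test. The 95% half-width of the planned test is 1.99 × √(2/40) = 0.45 SD. For the contrast, multiply by √(2(1 − ρ)); its power is that of a test with d = 0.5/√(2(1 − ρ)).

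| ρ | half-width (SD) | power at I = 0.5 |
|---|---|---|
| −0.3 | 0.72 | 0.28 |
| 0 | 0.63 | 0.35 |
| 0.3 | 0.53 | 0.46 |
| 0.5 | 0.45 | 0.60 |
| 0.7 | 0.34 | 0.81 |

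The planned test has 0.45 SD and 0.60, so the contrast is less precise whenever ρ is below 0.5.

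**When the contrast itself misleads.** (i) If the direct effect is 0.5 SD without hypnosis and 0.25 SD under it, with I = 0, the contrast estimates 0.25 − 0.5 = −0.25 SD and rejects in 12%, 15%, 20% or 30% of trials at ρ = 0, 0.3, 0.5 or 0.7. (ii) If half of an enhancement of 0.5 SD carries into the non-hypnotic run of the half of participants whose hypnotic run came first, the estimate is 0.5 × 0.25 + 0.5 × 0.5 = 0.375 SD. (iii) Section 6.2.2 schedules the HIP, a hypnotic induction, directly after rTMS and thus before the post-rTMS runs, and everyone has already had the pre-rTMS hypnotic run. Restricting to participants whose non-hypnotic run came first therefore removes only carry-over within the session.

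**The case against.** The trial tests augmentation. An add-on comparison, rTMS plus hypnosis against sham plus hypnosis, is a legitimate target, and section 9.6.2 frames the imaging analogue that way. This stands: a reader might infer that the rating test is biased or has an inflated error rate, and it does not for the effect of rTMS on pain under hypnosis. Only the step to enhanced hypnotic analgesia needs the extra assumption.

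The protocol also has a second reason to doubt a direct effect, the stimulation frequency, and section 2.2 says that inhibitory and excitatory stimulation of L-DLPFC move the network in opposite directions. A reader might take the analgesia that section 2.2 reports for L-DLPFC rTMS as evidence of a direct effect here. The documents do not support that: where they state the type of stimulation for those pain results, it is excitatory. A direct effect is open, not shown.

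The proposed contrast swaps one assumption for another, namely equal direct effects with and without hypnosis, which section 9.6.2 leaves open. It may have little power. It also needs ratings that the text does not confirm for the non-hypnotic runs. The wording of the non-hypnotic audio is not in the available text; if it carries an analgesic suggestion, those runs are not a plain control. All of this stands, so the contrast can only be supportive.

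The clinical outcome is not undefined: sections 1.1 and 9.7 name threshold. What is missing is the status of the rating test. The mediator analyses in section 9.7 bear on attribution but do not name these runs.

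**Conclusion.** The point holds in a limited form. The rating ANOVA soundly estimates the effect of rTMS on pain under hypnosis. Reading it as enhanced hypnotic analgesia requires D = 0, which the protocol infers from another stimulation site and itself qualifies. If D = 0, nothing changes. If D is 0.2 to 0.5 SD with no enhancement, the test is significant in 14% to 60% of trials at 40 per arm; these effect sizes are assumptions. A reader might infer that the non-hypnotic runs give a clean estimate of the direct effect, or that participants with the non-hypnotic run first are free of carry-over. The documents support neither, because of the unseen audio, the unconfirmed ratings and the HIP given between rTMS and the post-rTMS runs. The finding concerns the rating test only. Since section 9.2 stresses effect sizes for this hypothesis, it lies between minor and should-fix.

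**What to change.** 1. Keep the planned comparison and describe its result as the effect of active versus sham rTMS on pain under hypnosis. Label it supportive to the threshold outcome.
2. If ratings were recorded in both run types, add a supportive per-person score: [(non-hypnotic minus hypnotic rating) post-rTMS] minus [the same pre-rTMS]. Compare arms with a linear model that has run order as a covariate; section 9.7 plans a term for scan-session order only. Do not carry over the random-intercept model of section 9.2, which allows no person-level variation in change: in simulation at ρ = 0.5 it rejected in 1.1% of null trials and had power 0.38, against about 0.60 for the score.
3. Report the between-arm change in the non-hypnotic runs. Call it the direct rTMS effect only if the audio carries no analgesic suggestion. Give estimates and 95% confidence intervals for all three quantities.
4. State the limits: similar direct effects with and without hypnosis are assumed, precision is lower if ρ is below 0.5, and carry-over of hypnosis cannot be excluded in any participant.
5. If ratings were not recorded in the non-hypnotic runs, confine the conclusion to pain under hypnosis.

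The cost is wording plus one derived score, or wording alone. The SAP describes data collection in the past tense, so new ratings are probably out of reach.

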9.2 Sample Size and Randomization

For the power estimation, this study will use the significance level of .05 with two-tailed test. This study will recruit 100 individuals assuming about 20% missing data due to unusable imaging data and dropouts. In the Primary Mechanistic Hypothesis (formerly connectivity portion of Hypothesis 1a), power was estimated by focusing on the functional connectivity between DLPFC and dACC as the Primary Mechanistic Outcome. According to one prior study (47), the change in connectivity between DLPFC and dACC from pre to post rTMS is change in the quite large ($d=0.69$). We have augmented this one finding with numerous findings from other rTMS connectivity and functional activity studies, which demonstrated quite large effect sizes (see table 3 and table 4 below). Therefore, a somewhat conservative effect size of $d=0.8$ is being utilized for this study. The change from baseline to post-stimulation will be negligible in the sham rTMS group. Given this scenario, with the usable sample of 80 (40 rTMS, 40 sham), the estimated power is 0.8 ($\alpha=.05$, two-sided). For the Relevant Clinical Hypothesis (formerly Hypothesis 2b) and Secondary Hypotheses E (formerly Hypothesis 2a) as well as Secondary Hypotheses A, C, and D, both effect sizes and p-values will be monitored, with more emphasis on gathering information on effect sizes.

Manuscript	Site of Stimulation	Functional Connectivity Pair	Effect Size
Eldaief et al	L Posterior Intraparietal Lobule	rpIPL<->mPFC	0.72
Eldaief et al	L Posterior Intraparietal Lobule	rpIPL<->PCC	0.62
Nettekoven	Primary motor cortex	Primary Motor Cortex<->Premotor Cortex	0.9
Halko et al	Lateral cerebellum	DMN<->Posterior cingulate	1.26
Valchev et al	Primary somatosensory	Premotor	0.79

Vercammen Watanabe et al	Temporal-Parietal-Junction	Temporal-Parietal-Junction<->Right Insula	1.33
Watanabe et al	Left Motor Cortex	Left Motor Cortex<-> Right Motor Cortex	1.79
Watanabe et al	Left Motor Cortex	Left Motor Cortex<-> Right Motor Cortex	2

Table 3: Effect sizes for rTMS induced changes in functional connectivity as a surrogate for hypnotizability (Hoeft 2012)(31) modulated by rTMS(54, 56, 57, 158-160).

Manuscript	Stimulation Site	MRI/PET	Effect Size
Hubl	Frontal Eye Field	BOLD	0.4242
Bestmann	Motor/Somatosensory cortex	BOLD	2.36686405
Bestmann	Motor/Somatosensory cortex	BOLD	2.30589176
Cho	Right Dorsolateral prefrontal cortex	PET (CBF)	1.70333333

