9.6 Outcomes

9.6.1 Primary Outcomes

Primary Mechanistic Outcome Measure: *To determine the effect of active, inhibitory rTMS (cTBS) over L-DLPFC on modulating the connectivity of the neural network that underlies hypnotizability.*

This study will test an augmentation approach where one modality (rTMS) (30) is being used to modulate the neural circuitry underlying another technique (hypnotizability) in an effort that this combinatory approach may transiently produce the high hypnotizable phenotype on formal testing(31). It will be determined if modulation of the neural circuitry that underlies hypnotizability with rTMS can potentially produce a brain connectivity pattern that resembles a highly hypnotizable individual(31). This study proposes to measure the change in hypnotizability by contrasting the functional connectivity between the L-DLPFC and dACC at pre- and post-rTMS for both rTMS conditions (active versus sham cTBS) (31).

Hypnotizability Scans for Primary Outcome Measure: All participants will receive the same identical pre-rTMS resting state scan(31, 51). After randomization (to either active DLPFC rTMS or sham rTMS) where one half (n=45) will receive active DLPFC rTMS (cTBS), and one-half sham DLPFC rTMS (cTBS) (n=45)(30), all participants have their hypnotizability post-rTMS scan session(31, 51).

fMRI Preprocessing and Analysis: All fMRI data will be preprocessed and analyzed using FSL (FMRIB Software Library, version 5.0) (88). Physiological signals will first be removed using RETROICOR and RVHRCOR (97, 98). The first 6 volumes will be discarded to allow for signal stabilization. The following standard preprocessing steps will then be applied: motion correction using least square minimization (99), removal of non-brain tissues (100), resampling to 2 x 2 x 2 mm³ voxels, spatial smoothing with a 6 mm full-width at half-maximum (FWHM) Gaussian kernel to improve functional alignment between participants, and mean-based intensity normalization of all volumes by the same factor and high pass temporal filtering with a Gaussian-weighted least-squares straight line fitting, and linear registration using the FMRIB's Linear Registration Tool (FLIRT, 6 degrees of freedom (DOF)) to T1-weighted anatomical images and Montreal Neurological Institute (MNI) standard space.

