It is hypothesized that the rTMS modulation in hypnotizability(26) will result in greater hypnotic analgesia than sham rTMS. It is expected that a significantly greater mean increase across measures active rTMS than with the sham rTMS condition at the $p < 0.05$, level. This hypothesis will be tested with linear mixed modeling. It is hypothesized that the rTMS modulation will result in greater analgesia than sham rTMS. This study will measure the response to thermal pain stimuli at baseline and after active rTMS versus sham rTMS. In particular, it is hypothesized that the temperature necessary to produce threshold level heat pain during the pre-TMS period will not produce pain following active rTMS + HA. The temperature for evoking threshold and moderate pain will be assessed prior to and at 5-minute intervals for 30 minutes following the application of rTMS + HA. It is expected that the active rTMS stimulation + HA will temporarily eliminate pain following thermal stimulation at an intensity, which produced threshold level pain prior to rTMS + HA. It is also hypothesized that temperatures that produced moderate pain prior to rTMS will be significantly reduced following active rTMS versus sham. This hypothesis will be tested with linear mixed modeling and changes $p < .05$ are considered statistically significant.

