9.7 Data Analyses

The Primary Mechanistic Outcome Measure for this study is increased functional connectivity between the L-DLPFC and dACC. The Relevant Clinical Outcome Measure is change in hypnotic analgesia as measured by change in pain thresholds. For secondary aims, the emphasis is on identifying the magnitude of effects (clinical significance, effect size) instead of statistical significance. We will test whether the change in connectivity from baseline to post-treatment is greater in the active rTMS group as compared to the sham group. Following the convention in imaging studies, we will conduct our primary analyses treating the contrast (baseline versus post) as one univariate outcome. We do not expect much variation across our narrowly defined subjects, although some variation is still possible. Given that, we will also analyze the data in the linear mixed effects modeling framework (165, 166) allowing for random intercepts (although this is not customary in imaging studies) as a way of sensitivity analysis. The same analytical strategy will be used to test the effect of rTMS on the DLPFC and dACC activity, which is Secondary

Hypothesis A (previously activity portion of Hypothesis 1a-in grant), activity during conflict task (Secondary Hypothesis C), and during post-hypnotic instruction conflict task (Secondary Hypothesis D).

We are using thermal pain stimuli percept-matched to the individual receiving the intervention. Examining the treatment-effect moderating the role of the pain level is not a primary aim of this project.

Moderator/mediator investigation: We will explore various baseline variables as potential moderators of rTMS effect. For this investigation, we will employ the McArthur approach (167, 168) for moderator analysis. We will also examine potential mediators of rTMS effect using the McArthur approach (167, 168) as well as contemporary causal mediation approaches (169-174), which we believe will provide valuable insights regarding the neuromodulation mechanism for the next phase of investigation.

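### The clinical pain outcome has no consistent status and carries two or three unranked p<0.05 analyses, so a claim of enhanced analgesia could carry a false-positive chance of about 8 to 14%; the connectivity primary stays at 5%

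*Combined protocol and SAP*

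**What the plan says.** **Where the outcome sits.** The body heading is "9.6.1 Primary Outcomes", in the plural. Under it come the Primary Mechanistic Outcome Measure (connectivity) and then the Relevant Clinical Outcome. Secondary outcomes begin only in 9.6.2, and the clinical outcome is not among them.

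**How it is tested.** Section 9.6.1 states a 0.05 criterion three times for the clinical hypothesis:
- Change in pain ratings is compared by ANOVA: "It is expected that there will be a significantly greater mean decrease in pain ratings with the active rTMS + HA" than with sham, at the 0.05 level.
- A mean increase across measures, not further specified, is tested by linear mixed modelling at 0.05.
- After sentences on threshold-level and moderate-pain temperatures, the text closes with "This hypothesis will be tested with linear mixed modeling and changes $p < .05$ are considered statistically significant".

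**What other sections say.** Section 9.2 lists the Relevant Clinical Hypothesis with Secondary Hypotheses A, C, D and E and says of them all that "both effect sizes and p-values will be monitored, with more emphasis on gathering information on effect sizes". Section 9.7 names the clinical outcome beside the primary one, defines it as change in pain thresholds, and confines the effect-size emphasis to another group: "For secondary aims, the emphasis is on identifying the magnitude of effects (clinical significance, effect size) instead of statistical significance". Section 1.1 also defines it by pain thresholds. The SAP of January 4, 2024 describes all reported P values as nominal. It specifies tests only for HIP scores and for the blind.

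No section gives an order among the pain analyses, an alpha split, or a rule for which of them decides the clinical question.

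**The concern.** The same pain result could be presented as a significant finding under 9.6.1 or as effect-size information under 9.2. The choice of measure is also open: ratings, thresholds, moderate-pain temperature, or an unspecified set of measures. If these choices are made after the data are seen, a claim that rTMS enhances hypnotic analgesia can rest on whichever test crossed 0.05. The trial's title is about augmenting hypnotic analgesia, so readers will give weight to that claim whatever connectivity shows.

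**Working it through.** **The plan's own figure.** The documents state no family-wise error rate. The one error-related calculation is in 9.2: "the estimated power is 0.8 ($\alpha=.05$, two-sided", for d = 0.8 and 40 per arm. The check is 0.8 × √(40/2) = 3.578; 3.578 − 1.960 = 1.618; power = Φ(1.618) = 0.947 (0.942 with the noncentral t). The stated 0.8 is not reproduced; at 40 per arm it corresponds to d of about 0.63. That is a separate matter, and nothing below depends on it.

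**Inputs.**
- Level per test: two-sided 0.05. Section 9.2 says "this study will use the significance level of .05 with two-tailed test", and 9.6.1 repeats 0.05 for each pain analysis.
- Number of pain tests, k: 3 if the two mixed-model statements describe separate analyses, 2 if they describe one model. The text allows either.
- Correlation between the test statistics: not given. I assume 0 to 0.8. Measures on the same patients should be positively correlated, so 0 is an outer bound.
- The 5-minute repeats over 30 minutes count as part of one mixed model, not as extra tests.

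**Step 1: independent tests.** Chance of at least one false positive = 1 − 0.95^k.
- k = 2: 1 − 0.9025 = 0.0975
- k = 3: 1 − 0.857375 = 0.1426

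**Step 2: correlated tests.** Chance = 1 − P(all |Z| < 1.96), with equally correlated standard normal statistics, by simulation.

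| Pain tests | correlation 0 | 0.5 | 0.8 |
|---|---|---|---|
| 2 | 9.8% | 9.1% | 7.8% |
| 3 | 14.3% | 12.5% | 9.9% |

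At correlation 0.9 the figures fall to 7.0% and 8.4%, still above 5%.

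**Step 3: connectivity as a further route to success.** With three pain tests, all four independent: 1 − 0.95^4 = 0.185. If connectivity is uncorrelated with pain and the pain tests correlate at 0.5, 0.7 or 0.9, the figures are 16.9%, 15.4% and 13.0%. With two pain tests they are 14.3% (all independent), then 13.6%, 12.9% and 11.7%.

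**Step 4: one named clinical analysis.** k = 1 gives 5% for the analgesia claim, provided the analysis is not chosen from the results.

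**Can the named measure be analysed?** Section 9.6.1 plans threshold and moderate-pain temperatures before rTMS and every 5 minutes for 30 minutes after rTMS plus hypnotic analgesia. Section 6.2.2 measures thresholds before rTMS, to choose a moderate stimulus. Section 6.2.5 reuses that fixed stimulus after rTMS and lists no new threshold measurement. If the procedures sections describe what was done, the outcome defined in 1.1 and 9.7 has no post-rTMS value.

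**The case against.** The strongest reply is that the protocol does rank its outcomes. Section 1.1 identifies the Primary Outcome Measure as connectivity, sections 3, 9.1 and 9.7 keep it as the Primary Mechanistic Outcome Measure, and 9.2 powers nothing else. The table of contents gives 9.6.1 a singular title. The pain outcome is labelled clinical rather than primary, and 9.6.1 describes its aim as exploratory. The expectation of p<0.05 is also used for secondary outcomes in 9.6.2, so that wording does not make an outcome co-primary. All of this stands. A reader might infer from the plural heading that the trial has two co-primary outcomes and no hierarchy; the documents do not support that.

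The SAP's statement that P values are nominal also counts, since it points the same way as 9.2. But the SAP describes no pain analysis and does not withdraw the decision rule in 9.6.1, so the contradiction remains.

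Finally, the two mixed-model sentences may be one model. That is accepted, and is why the count is given as two or three. None of these points says which pain analysis answers the clinical question.

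**Conclusion.** The point holds for the clinical outcome only. Its status differs between 9.2, 9.6.1 and 9.7, its measure differs between 9.6.1 and the definition in 1.1 and 9.7, and it has two or three unranked tests at 0.05. If any one may support a claim of enhanced analgesia, the false-positive chance for that claim is about 8 to 10% (two tests) or 10 to 14% (three). This rests on the global null, two-sided 0.05 for each test, and assumed correlations from 0.8 down to 0.

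A reader might go further and say that the trial's headline error rate is 9 to 19%. The documents do not support this as a statement of fact. It requires that any significant result, connectivity included, makes the trial a success, and no section says so. The upper end also needs four independent tests, which is implausible for pain measures on the same patients. Connectivity taken as the single test that 9.2 powers stays at 5%. The activity measures that 9.1 and 9.6.1 attach to it, and its use on both scan days in the Précis, are not counted here.

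**What to change.** First reconcile 9.6.1 with 6.2.2 and 6.2.5 on whether heat-pain thresholds were measured after rTMS. If they were not, say so openly rather than let pain ratings take their place without comment.

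Then make 9.2, 9.6.1 and 9.7 agree:
1. Connectivity is the only primary outcome.
2. The clinical analysis is the active-versus-sham contrast in change in heat-pain threshold, the measure in 1.1 and 9.7, from one mixed model.
3. Pain ratings and moderate-pain temperature are supportive, with estimates and 95% confidence intervals and no significance criterion.
4. All clinical p-values are labelled nominal, consistent with 9.2 and the SAP.

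The SAP reports in the past tense that data were collected and analysed, so date the change and disclose it as post hoc. For the same reason I do not propose testing pain only after a significant connectivity result: a sequence written now would not be prespecified, and conditioning pain on connectivity is itself debatable.

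The cost is wording and disclosure. No more patients are needed and the connectivity test loses no power. The downside is that a pain result cannot be presented as confirmatory.
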